Initially, many surgeons used larger catheters (22Fr) to promote an open anastomosis, but some groups have found this to be associated with fossa navicularis strictures⁷. As a result, most surgeons now leave an 18 or 20 French Foley catheter to drainage for approximately 1 week post-operatively⁷. Interestingly, no study to our knowledge has assessed whether catheter size has an impact on continence, post-operative pain, and long term complication rates such as bladder neck contracture. We would expect urinary flow rates to differ based on urethral or catheter diameter according to Poiseuille's law, and several studies have shown this to be the case⁸.

In this study, we will randomize our RALP patients to either a 16 French or 20 French catheter to assess the effect of catheter size on post-operative catheter pain. Additionally, we will investigate pads per day, urinary flow rates, post-void residual urine volume (PVR), International Prostate Symptom Scores (IPSS) and Quality of Life (QoL) score, as well as long term complications. We hypothesize that patients with a smaller catheter will have improved pain scores and less opioid use. In terms of return to continence, we predict that use of a smaller urethral catheter will decrease flow rates and consequently protect against urinary leakage without higher risk of urinary retention. We expect this group to use less pads per day at the 6 week post-operative visit. We do anticipate a higher risk of bladder neck constriction (BNC) would be expected as well in the long term given the smaller diameter anastomosis.

Study Purpose and Objectives

The purpose of this clinical study is to assess the effect of catheter size on post-operative catheter pain, urinary continence, urinary flow rates, PVR, IPSS and QoL scores, as well as long term complications. The details of data collection are described in the "Data Collection Procedures" section below. Study objectives will be measured by:

Primary Outcome:

- Mean catheter related pain score on POD5-7

Secondary Outcomes:

- IPSS and QoL Scores at 6 and 12 weeks
- Opioid use after discharge until POD7
- Pads per Day at 6 and 12 weeks
- Urinary flow rate at 12 weeks
- PVR at 12 weeks
- Long-term complications at 12 weeks, 1 and 2 years

Risks and Benefits

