As with any major surgery done under general anesthesia, there is a certain amount of risk, including heart attack, stroke and death. Preoperative assessment of a patient's overall health is part of the surgical workup at Virginia Mason Medical Center. Prostatectomies, including those done with a robotic-assisted surgery system, are also associated with the risks of impotence, incontinence, bleeding, infection, and bladder neck contracture.

Restoration of erectile function varies by patient and can be supported through the use of medications such as Viagra and Cialis and other types of treatment such as intraurethral suppositories or intracavernous injections.

Urinary continence depends on the internal, involuntary sphincter and the voluntary striated external sphincter. The internal sphincter is removed during RALP, as it is anatomically at the junction of the prostate and bladder. Practicing Kegel exercises returns function to the external sphincter after RALP and leakage can be decreased or eliminated over several weeks or months.

We would expect catheter size to impact urinary flow rates according to Poiseuille's law, and several studies have shown this to be the case⁸. We also anticipate that risks of anastomotic stenosis may be influenced by catheter size. We anticipate return to urinary continence and pain scores may be influenced by catheter size, which is the purpose of the study. Specifically, if randomized to the 16Fr group, we anticipate a possible increased risk of decreased urinary flow or bladder neck contracture in the future. If randomized to the 20Fr group, we hypothesize a possible risk of increased catheter related pain and time to regain post-operative continence.

Study design

This is a physician-sponsored, randomized, prospective study of patients identified to receive RALP. Patients will be eligible for this study if they:

- Are identified as candidates for RALP
- Are greater than 18 years of age

Patients will be excluded from the study if they:

- Have filled a prescription for opioid medications in the last 2 months. This will be reviewed by the medical record prescription history.
- Have a known latex allergy or are suspected to have developed an allergic response to the latex catheter during their clinical course.
- In whom pre-operatively, the catheter is anticipated to be left in place greater than 14 days based on clinical decision

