- Have a significant deviation from the normal operative protocol such as significant bladder neck reconstruction or conversion to open (these patients will be considered a screen fail during the operation and will not be randomized to a certain catheter size)
- Have a history of pelvic radiation

In addition, patients who have a significant deviation from the normal post-operative course such as pulmonary embolism, myocardial infarction, stroke, or other major complications that are unrelated to study intervention but would impact outcome measures may be excluded from data analysis and further data collection per investigator's discretion.

Patient recruitment

Patients seen in pre-operative consultation by Virginia Mason Medical Center urologists will be assessed by the consulting surgeon for protocol eligibility at the time of consultation. The consent form will be reviewed with the patient in person, or by phone, at least 24 hours prior to surgery to allow time for consideration and questions. Patients may sign the consent anytime in the pre-operative setting before medication has been administered.

Early Termination

Patients may be discontinued from the study, per investigator's discretion, if any of the following conditions are met:

- Catheter remains in place greater than 14 days post operatively
- Lost to follow up (patient cannot be reached to schedule a follow up appointment after 3 attempts)
- Patient withdrawal of consent

Data Collection Procedures

Patient follow-up visits are routine and will occur at approximately 1, 6, and 12 weeks post operatively. Specific time point and methods of data collection are described below:

Post-surgical pain scores will be determined using a visual analog scale (VAS) with patients rating their mean post-operative pain on a scale from 1- No Pain to 10- Worst Possible Pain (Figure 1). Patients will be asked to indicate their pain specifically related to the catheter on this

scale. This information will be collected at POD7 just prior to catheter removal. This will be done in clinic if the appointment is that day or by telephone/mail/email/fax if the patient's appointment is not that day. A post-operative form including the VAS pain scale (Figure 1) and a pre-paid mailing envelop will be given to the patient in their study packet.

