Post Operative Complications will be recorded during the hospital stay or at clinic follow up visits and include any significant deviation from the normal post-operative course. Transient and permanent complications will be evaluated as part of this trial. At the long term follow up visits at 1 and 2 years, investigators capture long term complications such as bladder neck contracture.

Timing of Data Collection

Follow up visit #1 will occur 7 days +/- 7 following discharge, although as indicated above, pain scores and opioid use will be collected on POD7 regardless of clinic visit day. If the clinic appointment is not on POD7, we will collect this data by telephone or by mail. Timing of catheter

removal will be determined by the surgeon and is not affected by the study. Follow up visit #2 will occur 6 weeks +/- 4 weeks following discharge. Follow up visit #3 will occur 12 weeks +/- 5 weeks following discharge to account for patient availability. Patients will have annual follow-up thereafter and long term complications such as bladder neck contracture (BNC) will be recorded at 1 and 2 years post treatment (+/- 3 months). No other study data will be collected at these long term follow up visits. The specifics of how data will be collected and analyzed for each outcome are listed below.

Duration of Study participation

It is estimated that each patient who enrolls in the study and completes the routine follow-up visits will be participating for approximately two years.

Treatment Methodology and Statistical Considerations

Patients will be randomized by chance to either a 16 French or 20 French catheter in a 1:1 ratio. Subjects will be randomly assigned to either the standard of care or multi-modal group using Microsoft Excel ® randomization function.

A 2 year follow-up was chosen to allow for transient postoperative abnormalities to resolve so that the incidence of both transient and permanent complications can be evaluated.

Statistical evaluation of this study was completed by Axio during protocol development to ensure proper design and statistical power. We will use an ANOVA statistical variance model to test the hypothesis that the 20Fr group will have a higher mean pain score than the 16 French group. Secondary outcomes will also be measured with ANOVA analysis.

Sample Size and Accrual

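### A catheter kept in beyond 14 days can end a man's study follow-up after assignment, which could bias the secondary comparisons in either direction

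*Combined protocol and SAP*

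**What the plan says.** The 14-day threshold appears twice in the protocol, with different roles.

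- **Before surgery (Study design, exclusion criteria).** A man is excluded if he is one "In whom pre-operatively, the catheter is anticipated to be left in place greater than 14 days based on clinical decision". This is a baseline criterion and raises no difficulty.
- **After surgery (Early Termination).** The list opens "Patients may be discontinued from the study, per investigator's discretion, if any of the following conditions are met", and its first entry is "Catheter remains in place greater than 14 days post operatively". The wording is permissive, and it ends study participation as a whole.

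On the timing of catheter removal, Timing of Data Collection says that "removal will be determined by the surgeon and is not affected by the study". Treatment Methodology and Statistical Considerations says: "Patients will be randomized by chance to either a 16 French or 20 French catheter in a 1:1 ratio". The primary outcome is "Mean catheter related pain score on POD5-7".

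Under Post Operative Complications the plan says: "Transient and permanent complications will be evaluated as part of this trial". The background paragraph predicts that the smaller catheter will "protect against urinary leakage without higher risk of urinary retention", and it anticipates more bladder neck constriction in that arm.

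Data Analyses limits men lost to follow-up to the short-term analysis and handles other missing postoperative data case by case. No section keeps discontinued men in follow-up, and none defines an as-randomised analysis set.

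**The concern.** Discontinuing men on something that happens after assignment can undo the balance that randomisation provides. Here the trigger depends on a surgeon's decision and the removal on an investigator's discretion. With no masking described, either could vary with the catheter size used.

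The outcomes exposed are the ones the plan itself expects to differ by arm: continence and bladder neck contracture. The separate clause in the Study design section, on major postoperative complications, at least requires that the event be unrelated to the study intervention. The 14-day condition has no such requirement. In a trial of about 55 men, even a few removals could change a comparison of rare complications.

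**Working it through.** **1. The plan's own figure.** Sample Size and Accrual asks for 44 men with full participation after 20% dropout: 44 / (1 − 0.20) = 55 enrolled. At 1:1 that is 27 or 28 per arm. Discontinued men come out of the 55.

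**2. Which outcomes fall before and after the trigger.**

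- Pain covers days 5 to 7 and the opioid count runs to day 7. Both precede day 14. The plan does not say whether these data are kept for a discontinued man; I take them as kept.
- The week-6 visit is 6 ± 4 weeks after discharge, so the earliest is 2 weeks after discharge. For discharge on postoperative day 1 or later, that is day 15 or later.
- The week-12 visit opens 12 − 5 = 7 weeks after discharge. The 1- and 2-year visits come later still.

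The rule can therefore affect only what is collected from week 6 on: pads, IPSS/QoL, flow rate and residual volume where obtained, and long-term complications.

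**3. How many men.** The documents give no rate of stay beyond 14 days. Assuming 2% to 10% in both arms, 55 × 0.02 = 1.1 and 55 × 0.10 = 5.5, or about 1 to 6 men.

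**4. What removal could do to contracture.** The documents give no contracture rates either, so everything here is assumed. Let q be the share of an arm with prolonged stay, rP the contracture risk in those men (taken as equal in the two arms) and rN the risk in the others. With full follow-up the arm's risk is q·rP + (1 − q)·rN. If every such man is discontinued, it is rN.

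| Case | q, 16 Fr / 20 Fr | rN, 16 Fr / 20 Fr | rP | Full follow-up | Ratio, full | Ratio, removed |
|---|---|---|---|---|---|---|
| A | 15% / 5% | 5% / 5% | 5% | 5.0% / 5.0% | 1.00 | 1.00 |
| B | 10% / 10% | 5% / 5% | 25% | 7.0% / 7.0% | 1.00 | 1.00 |
| C | 15% / 5% | 5% / 5% | 25% | 8.0% / 6.0% | 1.33 | 1.00 |
| D | 5% / 15% | 5% / 5% | 25% | 6.0% / 8.0% | 0.75 | 1.00 |
| E | 5% / 15% | 10% / 5% | 30% | 11.0% / 8.75% | 1.26 | 2.00 |

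For case C, 16 Fr: 0.15 × 0.25 + 0.85 × 0.05 = 0.08. For 20 Fr: 0.05 × 0.25 + 0.95 × 0.05 = 0.06. The ratio is 0.08 / 0.06 = 1.33, and after removal 0.05 / 0.05 = 1.00.

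Case A shows no bias when prolonged stay carries no extra risk. In case B the ratio is right but the risk in each arm is understated (5% against 7%). Case C hides an excess with 16 Fr, case D hides an excess with 20 Fr, and case E exaggerates an excess with 16 Fr.

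**5. Precision.** In case C, 27.5 men per arm give 27.5 × 0.08 = 2.2 and 27.5 × 0.06 = 1.65 expected contractures. As a further illustration, take 3/22 against 1/22, a ratio of 3.0. The standard error of the log ratio is √(1/3 − 1/22 + 1/1 − 1/22) = 1.115. The approximate 95% interval is exp(1.099 ± 1.96 × 1.115), or 0.34 to 27. The trial could not distinguish any of the ratios in the table.

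**The case against.** The case for leaving the rule alone has several parts.

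- **The rule is optional.** An investigator may never use it. This stands: loss is possible, not certain. But discretion without described masking is itself a route to selection.
- **Prolonged stay may be benign.** A reader might infer that a catheter still in after 14 days signals a healing or voiding problem. No section says so. Visit 1 is 7 ± 7 days after discharge, and the schedule puts Day of Catheter Removal in that visit's column. A man discharged on day 1 and seen at the end of the window is at day 1 + 7 + 7 = 15, and could meet the condition through scheduling alone. This stands, and it is why the bias is conditional.
- **Retention.** A reader might infer that the removed men are those most informative about retention. The condition concerns a catheter that stays in, whereas retention shows itself after removal. A man re-catheterised after a failed void is not clearly covered.
- **Duration is already recorded.** Day of Catheter Removal is scheduled, and the complications paragraph already covers notable departures from the expected recovery. Prolonged stay can therefore be compared by arm. Later outcomes still cannot be recovered.
- **Few men, secondary outcomes, poor precision.** All true. Anticipated long stays and significant bladder neck reconstruction are excluded before randomisation, and the primary outcome is already in hand. This limits the importance of the point, but it gives no reason to keep a rule that protects neither the primary outcome nor the opioid count.

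**Conclusion.** The concern holds for the secondary outcomes. The protocol allows unmasked, discretionary discontinuation from the whole study on an event that follows assignment, and says nothing about following or analysing those men afterwards. Pain and opioid use are collected before the rule can apply.

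Bias in the later between-arm comparisons arises if prolonged stay is related to catheter size and to the outcomes. Its size and direction cannot be derived from the documents, and every rate in the working is an assumption. The working also assumes that every affected man is discontinued; partial use of the rule could do less, or could select further.

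A reader might go on to infer that contracture and continence data will be lost selectively and that 16 Fr will look falsely safe. The documents do not support that. The wording is permissive, no reason for prolonged stay is given, and cases C to E show that the distortion could favour either arm. The change is still worth making, because the rule offers no visible benefit and is cheap to remove.

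**What to change.** 1. Delete "Catheter remains in place greater than 14 days post operatively" from the Early Termination list. Keep the pre-operative exclusion for anticipated long stay.
2. State that men whose catheter stays in beyond 14 days continue all scheduled follow-up and are analysed in the arm to which they were randomised.
3. Use the Day of Catheter Removal already in the schedule to describe duration by arm. Record a complication only where the existing definition under Post Operative Complications is met; a long stay alone need not count as one.
4. Optionally, add a sensitivity analysis of 6-week pads and IPSS that omits these men.

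**Cost.** The amendment needs IRB review. No new visits are required, since the 1-, 6- and 12-week visits are routine and annual follow-up is already planned. The week-6 window opens 2 weeks after discharge, so pads and IPSS may be noisier or hard to interpret for a man whose catheter has just come out or is still in. The change does not affect when any catheter is removed.

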Opioid use will be collected at POD7 using the post operative pain form (Figure 1). Patients will be asked to count the number of pills left in their opioid prescription to determine number of tabs taken from discharge to POD7. If the patient is discharged after POD1, opioids taken as an inpatient on POD2 from the medical record will be included in opioid use. All opioid data will be converted a standardized morphine equivalency for comparison.

Pads per day: The patient will be asked to indicate the number of pads per days they are using. This data will be collected at 6 and 12 week follow up visits. This will be done in clinic if the appointment is that day or by telephone/mail/email/fax/REDCap (patients contact information, including email address, will be obtained from Cerner when available or by asking patient) if the patient's appointment is not that day. We recommend use of the Depend® Incontinence Guard for men (<https://www.depend.com/mens-solutions/products/10544>), or a comparable generic version.

International Prostate Symptom Score (IPSS) and Quality of Life Score: This validated questionnaire is an 8 question (7 symptom questions + 1 quality of life question) written screening tool used to screen for, rapidly diagnose, track the symptoms of, and suggest management of the symptoms of prostate disease. This is a clinician rated, validated scale. It will be administered and scores collected at the 6 and 12 week follow up visits. This will be done in clinic if the appointment is that day or by telephone/mail/email/fax/REDCap (patients contact information, including email address, will be obtained from Cerner when available or by asking patient) if the patient's appointment is not that day.

PVR: Post void residual volumes will be measured by having the patient void to their best effort (into a uroflowmeter described below) and then using a standard suprapubic bladder scanner to measure the remaining urine volume immediately after voiding. This will be measured at the 12 week follow up visit per investigator's discretion if clinically indicated.

Urinary flow rates will be measured by using a uroflowmeter. The patient voids into the device and is records the max flow rate, void time, and voided volume. This will be be measured at the 12 week follow up visit per investigator's discretion if clinically indicated.

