HUMAN SUBJECTS

Institutional Review Board (IRB) Review and Informed Consent

This protocol, the ICF and any subsequent modifications will be reviewed and approved by the IRB at Benaroya Research Institute at Virginia Mason. A signed ICF will be obtained from each subject.

Subject Confidentiality

All study data will be recorded in a password protected database. All computer entry and networking programs will be done using SID's only. Paper source will be stored in a secure location with access limited to study staff, Clinical Research Compliance Department staff, and outside regulatory bodies such as OHRP and FDA. Clinical information will not be released outside of the study team without written permission of the subject, except as necessary for monitoring by CRP Compliance, the FDA, and/or OHRP.

Study Modification/Discontinuation

The study may be modified or discontinued at any time by the Principal Investigator, IRB, OHRP, the FDA or other Government agencies as part of their duties to ensure that research subjects are protected.

PUBLICATION OF RESEARCH FINDINGS

Publication of the results of this trial will be governed by the policies and procedures developed by the Clinical Research Program. Any presentation, abstract, or manuscript will be made available for review by the Benaroya Research Institute prior to submission. No patient identifying information will be included in any publication or presentation of study results.

Figure 1 – Post-Operative Form

[figure not shown]
Virginia Mason Post-Operative Catheter Symptom Assessment

Name: _____

Date of Surgery: _____

Please fill out the following form on the 7th day after surgery (day of surgery is day 0, not 1)

1. Please circle your average catheter pain level at home within days 5-7 after surgery:

2. Please indicate how many tablets of opioids (oxycodone) you have taken at home (not in the hospital) in the first week since leaving the hospital. _____ tabs

Thank you for taking this survey. Please mail it back to Virginia Mason Urology using the pre-paid envelope included in your packet. If you lost the envelope, or you have questions, please call us at [contact].

REFERENCES

1. Centers for Disease Control (CDC). NATIONAL HOSPITAL DISCHARGE SURVEY. (2012).
2. Sammon, J. D. *et al.* Long-term follow-up of patients undergoing percutaneous suprapubic tube drainage after robot-assisted radical prostatectomy (RARP). *BJU Int.* **110**, 580–585 (2012).

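### Inpatient opioid doses from POD3 to discharge are counted nowhere, and the patient form does not collect what the opioid outcome needs

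*Combined protocol and SAP*

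**What the plan says.** Four places in the combined protocol and SAP describe this outcome.

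- **Study Purpose and Objectives, Secondary Outcomes:** "Opioid use after discharge until POD7". No inpatient part is mentioned.
- **Data Collection Procedures, opioid use:** using the Figure 1 form, patients are to "count the number of pills left in their opioid prescription to determine number of tabs taken from discharge to POD7". For men who leave later than POD1 an inpatient part is added: "opioids taken as an inpatient on POD2 from the medical record will be included in opioid use". The amounts are then to be converted to morphine equivalents.
- **Figure 1, Post-Operative Form:** the patient reports "how many tablets of opioids (oxycodone) you have taken at home (not in the hospital) in the first week since leaving the hospital". The same form is to be completed on day 7 after surgery, with surgery as day 0.
- **Schedule of procedures:** the row names home use only, in the Day 7 column.

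The Timing of Data Collection section fixes opioid collection at POD7 whatever the date of the visit. Opioid use is analysed by ANOVA like the other secondary outcomes, and the introduction predicts less of it with the smaller catheter.

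**The concern.** The inpatient clause appears meant to make men discharged on POD1 and POD2 comparable. It stops there. A man still in hospital on POD3 or later takes doses that are neither home tablets nor POD2 inpatient doses, and no section adds them. Two men with the same consumption can therefore receive different totals because of their discharge day alone.

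The form is the only stated means of collecting home use, and its opioid item does not match the procedures. It does not ask for the pill count, it names one drug, it has no field for tablet strength or any other opioid, and its reference period is anchored to discharge while its completion day is anchored to surgery. At stake is the validity of a named secondary outcome that carries one of the trial's hypotheses. The primary pain outcome is not affected.

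**Working it through.** The plan states no effect size, power or expected value for opioid use, so there is no figure to reproduce. The check is a comparison of the texts and a count of days.

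**Side-by-side reading**

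| Feature | Outcome list | Procedures | Form |
|---|---|---|---|
| Inpatient doses | not mentioned | POD2 only | excluded (home use only) |
| End of window | POD7 | POD7 | one week after discharge, but completed on POD7 |
| What is recorded | not stated | tablets left | tablets taken |
| Drugs | opioids | all, as morphine equivalents | oxycodone, no strength |

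**Days covered**

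Assumptions: POD k is one whole day occupying [k, k+1); use is constant at one unit per day; discharge is on POD d at fraction f of the day, so t = d + f. The reference window POD2–POD7 has 6 days.

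- Outcome list (home to POD7): 8 − t.
- Procedures: 8 − t, plus min(t, 3) − 2 if d > 1.
- Uncounted within POD2–POD7 under the procedures: max(0, t − 3).

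Mid-day discharge (f = 0.5), with the range for f from 0 to 1 in brackets:

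| Discharge | Outcome list, days | Procedures, days | Uncounted in POD2–POD7 | Share of 6 days |
|---|---|---|---|---|
| POD1 | 6.5 | 6.5 | 0 | 0% |
| POD2 | 5.5 | 6.0 | 0 | 0% |
| POD3 | 4.5 | 5.5 | 0.5 (0–1) | 8% (0–17%) |
| POD4 | 3.5 | 4.5 | 1.5 (1–2) | 25% (17–33%) |
| POD5 | 2.5 | 3.5 | 2.5 (2–3) | 42% (33–50%) |

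A POD1 discharge also contributes home doses from the rest of POD1 (0.5 day at mid-day, range 0–1), which no later discharge contributes. This matters for the fix.

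**Effect on a group mean**

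The documents do not give the distribution of discharge days. If a fraction p of patients loses a share s, the mean falls by p × s. For an assumed p = 10% and s = 17–50% (POD4 or POD5 discharge), that is 0.10 × 0.17 = 1.7% to 0.10 × 0.50 = 5%. It scales with p: half as many late discharges, half the effect; twice as many, twice the effect. It is larger if late discharges are heavier users.

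**Effect on the arm comparison**

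Let m20 and m16 be mean daily use, and u20 and u16 mean uncounted days, with use and stay unrelated within an arm. The observed difference over POD2–POD7 is

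6(m20 − m16) − (m20·u20 − m16·u16) = (6 − ū)(m20 − m16) − m̄(u20 − u16),

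where ū and m̄ are the averages over the two arms. With equal stays the second term is zero and the difference shrinks by ū/6, the same 1.7–5% under the assumption above. With unequal stays the second term can go either way.

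**Form window**

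Taking discharge at the start of the day, a literal week ends on POD7 for a POD1 discharge, POD8 for POD2 and POD9 for POD3. Completed on POD7 as instructed, the form covers 8 − t days, the same as the outcome list. It can run past POD7 only if it is completed late.

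**The case against.** The strongest case against is that this is a wording matter in an unpowered secondary outcome. Much of that case stands.

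- **Bias.** A reader might infer that the rule understates any arm difference. The documents do not support that. Allocation is 1:1 and nothing says that stay differs by catheter size. With balanced stays the loss is a small proportional shrinkage; if the 16 Fr arm stayed longer, the error would favour the hypothesis. Nor do the documents say that longer stays are more painful.
- **Form overrun.** A reader might infer that every form runs past POD7. It cannot when completed on the instructed day. The conflict matters only for late completion, which mailed return makes possible.
- **Conflicting definitions.** The form's restriction to home use can be read as complementary to the record-based inpatient count, and it avoids double counting. This is fair. It leaves the POD2 limit, the counting method and the missing fields as the real discrepancies.
- **Missing data fields.** Strength and other opioids might be recovered from the prescription history used for eligibility, or from the Day 7 medications review. That is possible, but no section links either source to this outcome.
- **Exclusions.** Some long stays may leave the analysis under the Study design clause on major complications. That clause is discretionary and limited to complications unrelated to the intervention, so a man kept in for catheter pain would remain.

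None of this supplies the inpatient doses from POD3 onward.

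**Conclusion.** The point holds as a measurement defect. Followed literally, the plan under-counts opioid use for men discharged on POD3 or later, by 0–1, 1–2 and 2–3 of six days for discharge on POD3, POD4 and POD5, assuming equal daily use. The form does not collect the pill count, or all the information needed for morphine equivalents, that the procedures call for. The overall effect cannot be found from the documents because the number of late discharges is not given. It is probably small, and the 1.7–5% figure rests on an assumed 10% of patients. The expected consequences are added noise and a slight proportional shrinkage of a per-day difference. Further bias, in either direction, would need length of stay to differ by arm. It is worth correcting because the remedy is specific and cheap.

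**What to change.** 1. **One definition.** State the same fixed window for all patients in the outcome list, the procedures, the form and the schedule: total morphine equivalents wherever taken, with every inpatient dose in the window, not POD2 alone, taken from the medical record.
2. **Reword the form item** to cover the time from leaving hospital until today (day 7 after surgery), with fields for tablets left, tablet strength and any other opioid.
3. **Put POD1 discharges on the same window.** Rewording alone would not do this, because their home tablets on POD1 would still be included. Either start the window at POD1 for everyone, with inpatient POD1 doses included, or keep POD2–POD7 and have the form record home tablets taken on POD1 separately so that they can be subtracted.

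Under either choice the uncounted inpatient days fall to zero whatever the discharge day. The cost is one form revision and chart abstraction from a source the plan already uses: late discharges only if the window stays POD2–POD7, or POD1 doses for all patients as well if it starts at POD1.
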